heart. Common manifestations include Raynaud's phenomenon, skin thickening, dyspnea and cough, gastroesophageal reflux and other gastrointestinal symptoms.⁵⁻⁷ Disease presentation is extremely heterogeneous, and the course of the disease is highly unpredictable.⁵⁻⁷ People with SSc commonly experience diminished hand function and mobility limitations, pain, fatigue, sleep problems, pruritus, symptoms of depression, and body image distress from disfiguring aspects (e.g., skin tightening, pigment changes, hand contractures, telangiectasias).⁸⁻¹³ Many people with SSc are at risk of serious complications from COVID-19 if infected due to lung involvement (> 40% have interstitial lung disease)¹⁴ and common use of immunosuppressant drugs.¹⁵

The Scleroderma Patient-centered Intervention Network (SPIN)^{16,17} COVID-19 Home-isolation Activities Together (SPIN-CHAT) Program is a 4-week (3 sessions per week) group videoconference-based intervention designed to improve symptoms of anxiety and other mental health outcomes among individuals with SSc at risk of poor mental health during the COVID-19 pandemic. The primary objective of the SPIN-CHAT Trial is to evaluate the effect of the program compared to waitlist control on Patient-Reported Outcomes Measurement Information System (PROMIS) Anxiety 4a v1.0¹⁸⁻²⁰ scores post-intervention among people with SSc with at least mild anxiety (baseline T-score ≥ 55). Secondary objectives are to evaluate the program's effects post-intervention on symptoms of depression, measured with the Patient Health Questionnaire-8 (PHQ-8)²¹; stress, measured with the Perceived Stress Scale (PSS)²²; loneliness, measured with the 6-item version of the UCLA Loneliness Scale (ULS-6)²³; boredom, measured with the 8-item version of the Multidimensional State Boredom Scale (MSBS-8)²⁴; physical activity, measured with the International Physical Activity Questionnaire – modified for the elderly (IPAQ-E)²⁵; and frequency of social interactions, evaluated with purposely designed items.

METHODS AND ANALYSIS

The SPIN-CHAT Trial is a pragmatic, two-arm partially nested RCT (PN-RCT)^{26,27} that will be conducted using the SPIN-COVID-19 Cohort. Pragmatic RCTs are conducted to replicate real-world delivery of interventions as much as possible and support decisions on

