Leisure activities that will be done at the start of each session will include games (e.g., Pictionary, charades, pub-style trivia), creative activities (e.g., roll-a-story, where participants roll a dice and take turns adding a sentence to a story; home scavenger hunt), cultural activities (e.g., virtual museum tours, name that tune), social activities (e.g., share your favourite recipe, share travel experiences, bingo with card created with activities the participants have used to stay active during the pandemic).

There will be an initial program overview in the first session. Then, educational segment topics will include (1) healthy information management and social connection (session 2); (2) managing worry (sessions 3, 7, 11); (3) relaxation strategies (sessions 4 and 8); (4) adapted home exercise (sessions 5, 9, 12); and (5) activity engagement at home (sessions 6 and 10). All educational segments will be supported by resource materials available to participants via an online SPIN-CHAT resource link.

In the healthy information management and social connection segment, strategies will be provided and discussion will be facilitated on how to stay informed via accurate information sources while avoiding sensationalist and other non-helpful information.⁵⁰ Information on using simple (e.g., phone) or more advanced technology (e.g., group videoconferencing) to stay connected will be discussed, along with strategies for connecting regularly with others.

The managing worry segments will include an overview of worry, including what it is, the difference between helpful and harmful anxiety or worry, how to identify triggers of worry, and strategies to manage worry, including identifying different types of worrying, using worry journals, worry postponement, and worry time.^{51,52} Exercises will be done with the group to illustrate techniques. In the relaxation segments, an introduction to the purpose of relaxation techniques will be presented, and participants will be guided through brief breathing, mindfulness, and visualization exercises.^{53,54} Adaptations for participants with breathing or positioning limitations will be made.

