The physical activity segments will include an overview of the physical and psychosocial benefits of physical activity for maintenance of health for chronic disease management,⁵⁵⁻⁵⁶ including mental health during the COVID-19 pandemic; movement guidelines to ensure safety; and how to monitor daily physical activity. Participants will be guided through movement options for the home-based setting, including warm-ups, aerobic, and strength activities. Behaviour change techniques to foster building the habit of moving more at home will be taught, including goal-setting, scheduling, addressing barriers, and building social support.⁵⁷⁻⁶⁰

Activity engagement sessions will be guided by the leisure education content model.⁶¹ Sessions will involve interactive group discussion about the benefits of leisure engagement⁶² for persons with SSc, addressing physical, social, emotional, intellectual and spiritual realms of health and wellbeing. Sessions will explore barriers to leisure for persons with SSc and include tips for finding leisure resources within the participants' own homes, both in-person and online.

Based on our previous experience^{48,49} and consistent with previous trials of videoconference training,^{63,64} 8 participants will be assigned to each training group to maximize effective interaction and participation. Sessions will be delivered using the GoToMeeting® videoconferencing platform, a high-performance platform that has been used successfully in similar applications^{65,66} and in feasibility and full-scale trials of SPIN's support group leader training program.^{48,49}

All group sessions will be video-recorded and audited to ensure adherence to the program by two members of the research team. We will use standard methods for evaluating intervention fidelity, including observation of entire sessions for a randomly selected sample of 25% of sessions. Members of the research team will evaluate adherence to each session's goals and content. Consistent with best-practice recommendations for assessing treatment fidelity,⁶⁷ this will be done using a checklist based on a standardized format adapted for the specific components of the SPIN-CHAT Program.

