Physical activity (IPAQ-E)²⁵: The 4-item IPAQ-E is a short-form version of the full IPAQ⁸⁴ designed to assess physical activity over the last week, including time spent sitting, walking, and in moderate and vigorous physical activity.²⁵ Compared to other short-form versions of the IPAQ, the IPAQ-E has examples of exercise specific to older adults. The full IPAQ has excellent reliability and moderate validity across many different countries,⁸⁴ and the IPAQ-E has similar validity.²⁵ The IPAQ is available in English and French.⁸⁵

Frequency of social interactions: Frequency of social interactions with others inside and outside of the home will be measured with 4 separate items, including (1) “On a typical day in the last week, how many times did you have a social conversation over the phone or a videoconferencing platform with one person?” (response = number of times); (2) “On a typical day in the last week, how many times did you have a social conversation over a videoconferencing platform with multiple people at the same time?” (response = number of times; not including SPIN-CHAT sessions); (3) “On a typical day in the last week, how long did you spend enjoying conversations with other individuals in the home?” (response = time); (4) “On a typical day in the last week, how long did you spend enjoying activities with other individuals in the home?” (response = time). Items (3) and (4) will only be displayed to participants who live with at least another person in their household.

Client Satisfaction Questionnaire (CSQ-8)⁸⁶: An adapted version of the 8-item version of the CSQ-8 will be administered to participants assigned to the SPIN-CHAT Program post-intervention in order to better understand how satisfied participants are with the program.

Adverse Effects will be assessed by ongoing monitoring during the trial and by asking participants post-intervention to describe any adverse experiences or outcomes that may have occurred.

Sample Size

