Effects of short anxiety-focused interventions in post-disaster settings are between 0.40 and 0.80 standardized mean difference (SMD).^{87,88} This is larger than estimated minimally important difference for the PROMIS Anxiety 4a v1.0 score (SMD = 0.23 to 0.34 SMD).⁷⁰⁻⁷³ For an assumed effect size of SMD = 0.50, a two-tailed test with $\alpha = 0.05$, and an intra-class correlation coefficient (ICC) of 0.05, N=146 provides $\geq 80\%$ power for our primary outcome, PROMIS Anxiety 4a v1.0; assuming 25% dropout, we will recruit 195 participants (98 in 12 SPIN-CHAT groups; 97 in the waitlist). We believe that this is a conservative power and sample size estimate. First, in cluster RCTs, ICC values for individual patient outcomes are typically lower than our 0.05 estimate.⁸⁹⁻⁹¹ If the true ICC is lower than our 0.05 estimate, this will result in greater power than estimated. Second, there has been no loss to follow-up in the feasibility trial or initial waves of our full-scale trial of the videoconference-based SPIN support group leader program,^{48,49} which has a similar design. Thus, we believe that a 25% loss to follow-up may be conservative.

Data Collection and Management

Questionnaires for the SPIN-COVID-19 Cohort, including outcome measures for the SPIN-CHAT Trial (baseline, 2-week interim, post-intervention), will be completed using the online surveying tool *Qualtrics*. This method has been used in the SPIN support group leader training program feasibility and full-scale trials.^{48,49} Limits on eligible values that can be entered will be set to reduce erroneous entries. Data for SPIN Cohort participants will be linked to SPIN Cohort demographic and medical data via the email that is used to login to both the SPIN Cohort and SPIN-COVID-19 Cohort platforms. To ensure accuracy, we have embedded a check into the *Qualtrics* survey tool to ensure that emails entered by SPIN Cohort participants match their SPIN Cohort platform login. Once online survey data is collected, data will be exported to the statistics software program STATA. Checking and cleaning of the data will occur within SPSS and be done by members of the study team. All information obtained about the participants during this study will be treated confidentially within the limits of the law. To protect

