The trial will be overseen by the SPIN Steering Committee along with the trial investigators and the SPIN-COVID-19 Patient Advisory Team. The Steering Committee will provide scientific direction for the RCT and will meet periodically to assess its progress. It will be responsible for RCT protocol execution, routine monitoring of data quality, recruitment and retention, and that the trial is meeting key milestones consistent with the timeline.

Risks and Potential Benefits of Participating in the SPIN-CHAT Trial

Participation in the SPIN-CHAT Trial will involve 3 weekly online training sessions for 4 weeks and completion of online measures. We do not anticipate any safety concerns with participation, although if there are any adverse events they will be reported to the local research ethics committee. Although it is hypothesized that the SPIN-CHAT Program will improve mental health outcomes, particularly symptoms of anxiety, it cannot be guaranteed that participants will receive any benefits from this study. However, information learned from this research may lead to more effective programs for at-risk individuals due to chronic medical conditions or for other vulnerable individuals during infectious disease outbreaks, which could result in benefits to others. There will be no financial compensation for participating in the SPIN-CHAT Trial, although the lottery provides an incentive for completing SPIN-COVID-19 Cohort measures, as described above.

ETHICS AND DISSEMINATION

The SPIN-CHAT Trial has been approved by the Research Ethics Committee of Centre intégré universitaire de santé et de services sociaux (CIUSSS) du Centre-Ouest-de-l'Île-de-Montréal (#2021-2286). All participants will provide electronic consent via *Qualtrics* prior to taking part in the study. Any modifications to the protocol which may have an impact on the conduct of the study, including changes of study objectives, study design, patient population, sample sizes, study procedures, or significant administrative aspects will undergo a formal amendment to the protocol. Any such amendment will be submitted to the Research Ethics Committee for approval and documented in the trial's registration.

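### The only stated direct question about harm comes at week 4; asking it also at the 2-week survey and the next cohort survey would reach people who stop attending sooner and would cover the final exercise session.

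*Combined protocol and SAP*

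**What the plan says.** The protocol's Trial Outcomes section describes harm ascertainment in one sentence with two routes: by continuing monitoring while the trial runs, and "by asking participants post-intervention to describe any adverse experiences or outcomes that may have occurred". No method, frequency, form or responsible role is given for the monitoring.

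Other parts of the protocol bear on what each route can reach:

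- **Sessions.** Under Intervention and Comparator the program runs three times a week for four weeks. Among the educational topics is "adapted home exercise (sessions 5, 9, 12". Of the physical activity segments the protocol says: "Participants will be guided through movement options for the home-based setting, including warm-ups, aerobic, and strength activities". They also teach participants to build a habit of moving more at home.
- **Stopping.** The same section lets participants stop attending whenever they choose. The escalation process described there concerns acute mental health issues and anything that worries a moderator. No contact on leaving is described.
- **Surveys.** Data Collection and Management lists questionnaires at baseline, 2 weeks and post-intervention, with no harm item stated for the 2-week one. The sections on the SPIN-COVID-19 Cohort and on Recruitment and Enrolment show that surveys go to both arms every two weeks through the cohort, whether or not a person attends sessions, and continue while the pandemic lasts.
- **Loss.** The Sample Size section sets recruitment "assuming 25% dropout".

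**The concern.** The monitoring route, as far as it is described, works mainly through contact in sessions. That leaves two places it cannot reach: people who have left the sessions, and the period after session 12. In both, the direct question is the main remaining source, and it is stated once, at the end of the program. A person who leaves in the first week would not be asked until week 4. An effect that develops some days after the last guided exercise, or from home exercise continued afterwards, may come after the only question.

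At stake is how much weight a report of few or no harms can bear. The anxiety comparison is not involved.

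**Working it through.** **1. Which session is last.** 3 sessions a week × 4 weeks = 12 sessions. Exercise falls in sessions 5, 9 and 12, so the last exercise session is also the final session.

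**2. Time from each exercise session to the week-4 question.** The protocol gives no session days. I assume the survey falls on day 28, counting the first day of the first session week as day 1, and try four weekly patterns. Session s falls on day 7 × floor((s − 1)/3) + the weekday number of that session; the gap is 28 minus that day.

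| Weekdays of sessions (assumed) | Day of sessions 5 / 9 / 12 | Days to the day-28 question |
|---|---|---|
| 1, 3, 5 | 10 / 19 / 26 | 18 / 9 / 2 |
| 1, 2, 3 | 9 / 17 / 24 | 19 / 11 / 4 |
| 2, 4, 6 | 11 / 20 / 27 | 17 / 8 / 1 |
| 5, 6, 7 | 13 / 21 / 28 | 15 / 7 / 0 |

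The ranges are 15–19 days for session 5, 7–11 for session 9 and 0–4 for session 12. Only session 12 is short of follow-up.

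**3. How many may not answer.** The plan's own figure reproduces: 146/(1 − 0.25) = 194.7, rounded up to 195, of whom 98 are in the intervention arm. If loss is equal across arms, 0.25 × 98 = 24.5, so 24 or 25 give no answer at week 4. The Abstract gives 162 randomised instead; with 81 per arm the figure is 0.25 × 81 = 20.25, about 20. (The 162 and the 195 need reconciling, but that is a separate matter.) The 25% is loss to follow-up; the protocol gives no rate for stopping sessions.

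**4. What non-response does to a report of no events.** The one-sided 95% upper bound with zero events among n people is 1 − 0.05^(1/n). For n = 98 it is 3.0%; for n = 73 it is 4.0%. This assumes that non-response is unrelated to harm. If harmed people respond less often, the reported rate would be too low, but the documents give neither a harm rate nor a response rate among those harmed, so I put no figure on it.

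**5. What repeating the question changes.** Take the interim survey at day 14 and the next cohort survey at day 42.

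- Session 12: 42 minus day 24 to 28 gives 14–18 days, instead of 0–4.
- Session 5: 14 minus day 9 to 13 gives a first question after 1–5 days, instead of 15–19.
- Someone who leaves after a first session on day 1 is asked after 13 days instead of 27.

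**The case against.** The strongest reply is that the plan does more than ask once, and most of it stands.

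- **Monitoring is the first route named.** A reader who starts at the post-intervention question might infer that it is the only ascertainment. It is not, although its method is undescribed.
- **People who stop are not lost.** A reader might infer that those who quit early are missed and that any harm statement would come from completers only. The documents do not support this. Surveys go out through the cohort regardless of attendance, with reminders and a lottery for completing every assessment, and the analysis is by intention to treat.
- **Session 12 is observed.** It is a live, moderated and recorded videoconference, and open discussion is listed after the educational segment. A fall or breathlessness during it could be seen or voiced. Only delayed effects lack a stated question.
- **Distress is already measured.** The anxiety and depression scales are scheduled at 2 and 4 weeks.
- **The loss figure may be high.** The Sample Size section says 25% may be conservative and reports no loss in a related videoconference program. Even at 25%, the zero-event bound moves only from 3.0% to 4.0%.
- **Timing is partly inferred.** The Abstract attaches immediate timing to the primary outcome; the adverse-effects sentence says only that the question is asked post-intervention.

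A reader might also see a contradiction between a population in which "> 40% have interstitial lung disease" and the statement "We do not anticipate any safety concerns with participation". There is none. Exercise is described as adapted and comes with safety guidance, and the same sentence on risks says that any adverse events go to the ethics committee.

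What the reply does not answer is that observation in sessions ends when a person leaves or the program ends, and that no earlier or later direct question is stated although suitable surveys already go out.

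**Conclusion.** The point holds as a minor one. The only stated direct harm question is at week 4. People who stop attending are asked late rather than missed, and those it misses are survey non-responders: about 24 or 25 of 98 at the planned 25%, possibly fewer. Delayed effects of session 12 have about 0–4 days of solicited follow-up, and nothing later is stated.

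This rests on three assumptions: session days like those tried above, a survey on day 28 (the protocol does not say how each person's two-weekly cohort cycle lines up with the start of a group), and loss that is equal across arms. One caveat applies: most row labels of Figure 2 are missing from the text available, so it can neither confirm nor exclude a further harm item.

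The stronger conclusion, that harm reporting would be limited to completers or that the last exercise session goes unobserved, is not supported. The sample size and the primary analysis are unaffected.

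**What to change.** In the Adverse Effects paragraph of Trial Outcomes and in Figure 2, state that the existing open adverse-experience question is asked of both arms three times: in the 2-week interim survey, at week 4, and in the next two-weekly cohort survey. The present sentence is not limited to one arm, so naming both arms is a clarification.

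People who stop attending would then be asked sooner, and session 12 would have about two weeks of follow-up. The third question depends on the cohort surveys still running, which the protocol ties to the length of the pandemic. For late groups, the report should also say whether waitlist participants had begun the program by then.

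The cost is about a minute more per survey, a short protocol change, and somewhat more minor events reported in both arms. No visit is added.

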whether interventions should be provided in practice.²⁸⁻³⁰ The trial will be a PN-RCT because participants randomised to the intervention arm will be clustered into intervention groups, and members of each intervention group will interact during videoconference sessions; participants randomly assigned to the waitlist control will not be clustered and will only complete trial measures. The reason that we will use a waitlist control arm and provide the program to people in this arm post-trial is that our patient organization partners are invested in providing access, and this is important for them to support the trial. It may also increase willingness to enrol in the trial by potential participants.

The trial has been registered (clinicaltrials.gov, NCT04335279), and the protocol follows recommendations for reporting from the SPIRIT (Standard Protocol Items: Recommendations for Interventional Trials) 2013 Statement.³¹ Results will be reported in accordance with standards described in the Consolidated Standard of Reporting Trials (CONSORT) statement³² and CONSORT extensions for nonpharmacologic trials,³³ cluster trials,³⁴ pragmatic trials,²⁸ and the draft extension for RCTs conducted using cohorts and routinely collected health data, which is forthcoming.³⁵ Initial participant enrolment and randomisation of participants is planned for April 2020.

SPIN-COVID-19 Cohort Participants

SPIN is a collaboration of SSc researchers, health care providers, people living with SSc, and patient organizations from Canada, the United States, Europe, Mexico and Australia that has assembled a large multinational patient cohort to collect longitudinal data on patient-reported outcomes in SSc and as a framework for embedding RCTs of e-health interventions.^{16,17} To be eligible for the SPIN Cohort, patients must be classified as having SSc based on 2013 American College of Rheumatology/European League Against Rheumatism criteria,³⁶ confirmed by a SPIN physician; be ≥ 18 years old; be able to give informed consent; be fluent in English, French, or Spanish; and be able to respond to questionnaires via the internet. The SPIN Cohort is a convenience sample. Eligible SPIN Cohort patients are recruited at SPIN

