In addition to describing the study, the consent form will explain (1) that eligible participants who enrol will be randomly selected on a rolling basis to be included in the trial whenever there are enough participants enrolled to form additional intervention groups on particular days and times in English or French; (2) that those randomly selected will be randomly assigned to an intervention group or to the waitlist with a 1:1 allocation ratio; (3) that participants randomised to the SPIN-CHAT Program plus those allocated to the waitlist will complete measures online every two weeks as they would anyway as SPIN-COVID-19 Cohort participants; (4) that, depending on the number of participants who enrol with availabilities based on language, days, and times, it is possible that some enrolled participants will not be randomised; and (5) that, enrolled participants who do not receive the intervention as part of the trial, either because they are selected for the waitlist or because they are not selected for the program or the waitlist, will be offered the program post-trial if still relevant, pending development of the COVID-19 situation. A member of the SPIN research team will call all potential participants to confirm eligibility, day and time availability, and desire to participate in the trial, prior to completing enrolment.

Random Selection and Allocation

SPIN-COVID-19 Cohort participants who provide consent for participation will be entered into different pools based on their availabilities and taking into consideration time zone differences. Figure 1 illustrates the flow of participants into the trial, and Figure 2 the schedule of enrolment, interventions, and assessments. Once there are enough participants to complete an intervention group and assign an equal number of participants to waitlist control, a third-party randomisation service will randomly select eligible participants and randomly assign selected

participants to the intervention group or waitlist control. This process will be repeated until trial enrolment is complete.

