SPIN personnel will provide the external service with an anonymised list of participants (only ID numbers will be provided) who could participate in an intervention group based on language and day and time availabilities. For each intervention group and waitlist control pairing, the service will randomly select 16 participants from the pool of enrolled participants available based on language, day, and time and will randomly allocate 8 to the intervention group and 8 to the waitlist group using block randomisation. One randomisation block will include 18 participants (9 intervention, 9 waitlist) to accommodate the total number that we anticipate randomising (see section on sample size).

All participants who are randomised will receive an email to communicate their assignment to the SPIN-CHAT Program or waitlist control. A second email will be sent to those allocated to the intervention arm with the date and time of their first group session and information on how to login to the videoconferencing system and online chatroom.

Blinding and Protecting Against Sources of Bias

A potential concern is that participants and the research team members will not be blinded to intervention status. In most pragmatic trials of education and psychological interventions, including the SPIN-CHAT Trial, participants cannot be blinded. This is understood as part of the response to being offered a treatment, similar to what occurs in clinical practice.^{28,30} A second concern relates to the potential for contamination if participants randomised to the SPIN-CHAT Program share program material with participants in the waitlist control. To attempt to minimize the influence of possible contamination, we will explain this concern to participants in the intervention arm of the trial and ask them not to share material or discuss the sessions with others outside of their intervention group during the trial.

Intervention and Comparator

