the participants' privacy, upon inclusion in the SPIN-CHAT Trial, a unique participant identification number will automatically be assigned to each participant. An encrypted database will be created, which will include the participant identification number and name. Data security measures in place at Qualtrics are described in the Qualtrics security statement.⁹² Information obtained from the survey and video recordings of the training sessions used to evaluate fidelity to program will be kept for 10 years on encrypted hard drives. During the trial, access to the data will be limited to the study investigators. Once trial results are reported, de-identified data will be made available upon reasonable request. No biological specimens will be collected.

Data Analysis

Analyses will be conducted by a statistician blind to trial arm allocation. For the primary outcome analysis (PROMIS Anxiety 4a v1.0), we will use an intent-to-treat analysis that compares all patients randomly assigned to the SPIN-CHAT Program to all patients assigned to the waitlist control. The intervention effect at 4 weeks will be estimated using a linear mixed model, adjusted for baseline PROMIS Anxiety 4a v1.0 scores. The model will include a random effect to account for clustering of participants in the training groups, but not for participants in the waitlist control arm, because there is no clustering in the control arm.^{26,27} We will investigate the effects of missing data using multiple imputation. As a secondary analysis, we will additionally adjust for age, sex, baseline loneliness, baseline boredom, and baseline physical activity. Analyses of secondary outcomes will similarly be done (1) controlling for baseline scores only and (2) controlling for baseline scores, age, sex, and other key baseline measures. Statistical significance for all analyses will be determined based on two-sided $\alpha = 0.05$. In addition, we will use complier-average causal effect analysis to estimate effects among patients who use the intervention at different levels compared to similar patients in the waitlist arm of the trial.⁹³

Data Monitoring

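### Randomisation is blocked in paired intervention and waitlist sets, but no analysis model has a block term, so the test is conservative and loses power if blocks differ

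*Combined protocol and SAP*

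**What the plan says.** **Allocation.** Under Random Selection and Allocation, consenting participants are "entered into different pools based on their availabilities and taking into consideration time zone differences". Randomisation is triggered set by set: "Once there are enough participants to complete an intervention group and assign an equal number of participants to waitlist control". For each pairing, "the service will randomly select 16 participants from the pool of enrolled participants available based on language, day, and time", and these are allocated 8 to the program and 8 to the waitlist by block randomisation. One block is larger, at 9 and 9. The consent description in Recruitment and Enrolment says that participants are "randomly selected on a rolling basis to be included in the trial whenever there are enough participants enrolled to form additional intervention groups", so blocks also follow one another in calendar time.

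**Analysis.** Under Data Analysis, the primary model has arm, baseline PROMIS Anxiety and a random effect for training group, "but not for participants in the waitlist control arm, because there is no clustering in the control arm". The adjusted model adds age, sex, and baseline loneliness, boredom and physical activity. For the other outcomes, "Analyses of secondary outcomes will similarly be done (1) controlling for baseline scores only", and then with age, sex and unnamed key baseline measures. Block, language, time slot and calendar period are not named in any model.

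**Design rationale.** The opening of Methods and Analysis explains that "participants randomly assigned to the waitlist control will not be clustered and will only complete trial measures".

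**The concern.** The reason given for leaving the control arm without a random effect concerns interaction: waitlist participants never meet. That is correct, but it is not the only source of shared outcome. Each waitlist set shares a randomisation block with its paired intervention group, and so shares language, time slot, often time zone, and a calendar period in the outbreak.

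A block effect common to both arms drops out of the arm difference. A model without a block term cannot see this. It reads the block effect as training-group variance in the intervention arm and as residual variance in the waitlist arm. The treatment estimate remains unbiased and the false-positive rate does not rise. What is at stake is precision: the reported standard error is too large, the confidence interval too wide, and power falls in a trial sized for about 80%.

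That blocks may differ is an inference from the pooling and the rolling selection. The documents report no block variance.

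**Working it through.** **1. Inputs.** From Sample Size: SMD 0.50, two-sided alpha 0.05, ICC 0.05, 146 analysed, 25% dropout, 195 recruited in 12 intervention groups. From Random Selection and Allocation: blocks of 8+8 and one of 9+9. The number of blocks is not settled: Sample Size gives 12 groups, while the 162 randomised in the abstract equals 9 × 16 + 18, which is 10 blocks. Both are shown. Assumed, because the documents are silent: block share of outcome variance after baseline adjustment of 0, 0.02, 0.05 or 0.10.

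**2. The plan's own figure.** With the design effect in the intervention arm only, n per arm = (1.960 + 0.842)² / 0.50² × [1 + 1 + (m − 1) × 0.05], where m is the analysed group size. At m = 7 this is 31.40 × 2.30 = 72.2, so 73 per arm and 146 in total. Then 146 / 0.75 = 194.7, so 195. The plan's figures are reproduced. Seventy-three per arm is about 6 per block over 12 blocks and about 7 over 10.

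**3. Variance with and without the block.** Let B, U and E be block, group and residual variance with B + U + E = 1, J blocks and m analysed per arm per block.

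- True variance of the arm difference: (U + 2E/m) / J. B does not appear.
- Variance the planned model reports, approximately: (B + U + E/m) / J + (E + B) / (Jm).
- Excess: B(1 + 1/m) / J, positive whenever B > 0.

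Example with U = 0.05, J = 12, m = 6, B = 0.05, E = 0.90:

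- True: (0.05 + 0.30) / 12 = 0.0292.
- Planned: (0.05 + 0.05 + 0.15) / 12 + 0.95 / 72 = 0.0208 + 0.0132 = 0.0340.
- SE ratio: √(0.0340 / 0.0292) = 1.08.

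At B = 0.02 the variances are 0.0300 and 0.0319 (ratio 1.03). At B = 0.10 they are 0.0278 and 0.0375 (ratio 1.16). With J = 10 and m = 7 the three ratios are 1.04, 1.09 and 1.18.

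**4. Simulation.** REML fits of the planned model and of a model with a random block intercept shared by both arms plus the group effect in the intervention arm; 20,000 runs per cell, Satterthwaite degrees of freedom in both, U = 0.05. Each pair is planned vs block term.

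| Block share | SE ratio, 12 blocks | Type I error (%), 12 blocks | Power (%), 12 blocks | SE ratio, 10 blocks | Power (%), 10 blocks |
|---|---|---|---|---|---|
| 0 | 1.02 | 4.5 vs 4.8 | 79 vs 80 | 1.01 | 75 vs 76 |
| 0.02 | 1.03 | 4.2 vs 4.9 | 78 vs 79 | 1.03 | 74 vs 76 |
| 0.05 | 1.08 | 3.3 vs 4.4 | 76 vs 79 | 1.08 | 72 vs 76 |
| 0.10 | 1.15 | 2.5 vs 4.3 | 73 vs 80 | 1.16 | 68 vs 78 |

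The SE ratio is the planned model's SE over the true SE. Bias was within 0.003 throughout. With 10 blocks, Satterthwaite type I error of the block model was 4.4 to 5.2%.

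**5. Sensitivity.** A separate simulation with 12 blocks of 8+8, 25% dropout at random and z tests gave power of 76.6 vs 80.1% at block share 0.05 and 74.9 vs 81.6% at 0.10. With no group variance (U = 0, 12 blocks, Satterthwaite), the power gap was 0.6, 1.3, 2.9 and 6.8 points at block shares 0, 0.02, 0.05 and 0.10.

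**The case against.** The strongest objection is about size. The planned model has one random effect in the intervention arm, so the ICC of 0.05 in Sample Size could be read as block and group variance together. Holding group ICC at 0.05 and adding block variance puts the total at 0.10 or 0.15 in the last two rows, and the protocol itself expects ICCs below 0.05. With the total fixed at 0.05 (z tests), power is 81.6 vs 83.3% at block share 0.02 and 82.3 vs 85.0% if all of it is block variance (12 blocks); with 10 blocks it is 78.8 vs 80.6% and 79.6 vs 82.6%. This stands as a limit: on that reading the gap is at most about 3 points. On the group-only reading the table above applies.

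Second, everyone meets the same anxiety threshold and baseline anxiety is already in the model, so residual block differences may be small. That also stands. Baseline adjustment cannot, however, remove changes in outbreak conditions during the following 4 weeks.

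Third, the gain depends on the reference distribution. With z tests the block model's type I error is 5.1–5.5% (12 blocks) or 5.4–5.8% (10 blocks). With a strict t on blocks minus one it is 3.0% and power is 72.7% (12 blocks, 25% dropout, block share 0.05), below the 76.6% of the planned model under z. This is a reason to name the method, not to omit the block. Part of each power gap also reflects unequal type I error, and at zero block variance there is no real efficiency to recover.

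Finally, the quoted sentence is not false. It is incomplete.

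**Conclusion.** The concern holds. The trial randomises within paired blocks and analyses as if it did not. If block means differ after baseline adjustment, the planned test is conservative: with group ICC 0.05, the standard error is overstated by about 3% at block share 0.02, 8% at 0.05 and 15–16% at 0.10. Under Satterthwaite, the power lost is 1, 3 and 7 points with 12 blocks and 2, 4 and 10 points with 10 blocks. It is negligible at a share of 0.02 or less.

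The block share is an assumption throughout, and the calculations also assume equal residual variance in the two arms. This is a loss of efficiency and calibration, not bias or excess false positives. The change should be made, but the trial's validity does not depend on it. Confidence is medium because the block variance is unknown.

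**What to change.** 1. Add randomisation block as a random intercept shared by both arms in the primary, adjusted and secondary-outcome models. Keep the training-group random effect in the intervention arm only.
2. Name Satterthwaite or Kenward-Roger degrees of freedom, because there are only 10 to 12 blocks.
3. Keep the sentence in Data Analysis but qualify it: waitlist participants have no clustering caused by the program, but they share a randomisation block with their paired group.
4. State that the block identifier created at randomisation is kept in the analysis dataset. On its own it does not reveal arm, so it does not affect the statistician's blinding.

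The cost is one variance term and one identifier that the randomisation service already generates. When blocks did not differ, simulated power did not fall (80% with the term vs 79% without for 12 blocks; 76% vs 75% for 10). The change should be fixed before outcome data are analysed.
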